## 7 Study Procedures and Schedule

### 7.1 Study Procedures/Evaluations

#### 7.1.1 Study Specific Procedures

##### Aim 1: Codesign Workshop

###### **Screening/Informed Consent**

- Screen potential subjects by inclusion and exclusion criteria until 8 family caregivers are consented (via HIPAA-compliant Zoom) and formally enrolled in the study and an additional 8 family caregivers meeting the inclusion/exclusion criteria are identified and recorded in a waitlist.

###### **Baseline/enrollment data collection**

- One 1:1 data collection session will be scheduled and completed with each co-design workshop participant at baseline/enrollment. This can be completed during the Zoom call to obtain informed consent with the caregiver participant's agreement or scheduled at a later time.

###### **5-Week Codesign workshop**

Caregiver participants will attend 5 weekly group co-design sessions (90-120 minutes/session) to discuss the following topics:

- *Session 1: family education videos*
- *Session 2: assessments and care plans*
- *Session 3: caregiver education articles and communication guides*
- *Session 4: mobile push notification or text messages to motivate/encourage caregivers*
- *Session 5: final design and features of the mHealth app; ways to best engage other family members in delirium care*

*Sample materials to show caregiver subjects in the co-design sessions are provided in Attachment A.*

**Optional User Testing:** An optional 30-minute, 1:1 user testing session will be scheduled with 5-6 volunteers from Aim 1 participants and waitlist on a first come first serve basis to test the beta version of the new caregiver mHealth app developed based on co-design workshop feedback before starting the Aim 2 pilot feasibility trial.

##### Aim 2: Pilot Feasibility Trial

###### **Screening/Informed Consent**

- Screen potential subjects by inclusion and exclusion criteria until 30 primary caregivers are consented and formally enrolled in the study

CONFIDENTIAL

This material is the property of the NYU Langone Health. Do not disclose or use except as authorized in writing by the study sponsor

- Optional: enrolled caregivers (“primary caregivers”) can choose to invite additional relatives or friends to join the study as “secondary caregivers”, who will also need to meet the inclusion/exclusion criteria and provide informed consent to participate in the study
- Obtain informed consent: n=30 primary caregivers + up to 30 secondary caregivers

**Week 0 Baseline/Enrollment Visit, n=30 primary caregivers + up to 30 secondary caregivers**

- Collect baseline caregiver demographics, health literacy, caregiving self-efficacy, comfort with technology, strain, \*depressive symptoms, burden, delirium knowledge, and DSD caregiving mastery in an online survey questionnaire in REDCap; all information being collected is based on caregiver report.
- Collect caregiver reported PLWD demographics, dementia type/severity, comorbidity, behavioral symptoms, and medications using anonymous (no PLWD identifiers being collected in this study) online survey questionnaires in REDCap.

**Week 1-Week 2 Intervention – Caregiver Education: n=30 primary caregivers + up to 30 secondary caregivers**

- Caregivers complete self-paced educational videos on DSD and how to administer a brief delirium screener, the Family Confusion Assessment Method

**Week 2 Visit (Immediately Post Training): n=30 primary caregivers + up to 30 secondary caregivers**

- Collect data on caregiver participants’ delirium knowledge and DSD caregiving mastery in an online REDCap survey questionnaire.

**Week 3-Week 6 Intervention Implementation: n=30 primary caregivers + up to 30 secondary caregivers**

- Caregivers complete weekly delirium screening using the Family Confusion Assessment Method in the study mHealth app.
- Caregivers implement a care plan consisting of delirium prevention or management tasks tailored to their loved one’s delirium risk factors.

**Week 6 Final Visit (n=30 primary caregivers + up to 30 secondary caregivers)**

- Collect data on caregiver participants’ delirium knowledge, DSD caregiving mastery, caregiver strain, depressive symptoms, burden, program satisfaction, and app usability in an online REDCap survey questionnaire.

Also see Attachment C for schedule of events.

\*We will stick with CES-D to collect data on depressive symptoms. We were considering replacing it with PHQ-9 because PHQ-9 is a shorter questionnaire. We decided to still use CES-D because it does not ask about suicidal ideation. All de-identified baseline caregiver depressive symptom raw scores will only be analyzed as a group and presented as mean/sd/range (or median/interquartile range/range if not normally distributed).

If a high level of symptoms are found from CES-D, such as depressive symptoms, we will offer to refer subjects to support services that may help with these, such as the NYU Alzheimer’s Caregiving Program. This information will remain confidential and will not be shared with others.

CONFIDENTIAL

This material is the property of the NYU Langone Health. Do not disclose or use except as authorized in writing by the study sponsor

If a high level of caregiving strain is found, we will offer to refer subjects to support services that may help, such as the NYU Alzheimer's Caregiving Program, however this information will remain confidential and will not be shared with others. If the depressive symptom score has increased for 15 or more points from the baseline/enrollment visit for a subject, our medical monitor, [name], (a board-certified nurse practitioner) will call the subjects to better understand their change in depressive symptoms; determine whether it is related to their study participation; and will refer them to mental health or emergency services as needed.

*Rationale for change score:* We will calculate the mean and range of the change score from baseline to posttest as a group (=all caregivers' scores lumped together).

If the upper limit of the range of the group change score is below 15, then it means that no one in the group has a substantial increase in their depression score and we will not reach out to any participants about their depressive symptoms.

If the upper limit of the range of the group change score is 15 or above (out of the 60-point CES-D scale), we will look up the participants who have a change score  $\geq 15$  and notify the medical monitor.

We only care about the change score because for people who have both high baseline and high posttest scores, it just shows that their baseline symptoms have not gotten better or worse over the study period.

### **7.1.2 Standard of Care Study Procedures**

Not applicable.

## **7.2 Laboratory Procedures/Evaluations**

Not applicable.

### **7.2.1 Clinical Laboratory Evaluations**

Not applicable.

### **7.2.2 Other Assays or Procedures**

Not applicable.

### **7.2.3 Specimen Preparation, Handling, and Storage**

Not applicable.

### **7.2.4 Specimen Shipment**

Not applicable.

## **7.3 Study Schedule**

All visits will be completed through phone or Via HIPAA-Compliant Zoom.

### **7.3.1 Screening**

- I. Pre-Screening Phase
  - a. Potential participants will call or email the PIs using the contact information provided in the recruitment email or mail.
  - b. PIs will take the participant's phone call or reply to the inquiry email and explain the study and answer questions. If a potential participant is interested and wishes to proceed, PIs will set up a formal screening appointment with the potential participant.

CONFIDENTIAL

This material is the property of the NYU Langone Health. Do not disclose or use except as authorized in writing by the study sponsor

- c. If the potential participant leaves a message, PIs will return their call and explain the study and answer questions within 2 business days. If the potential participant is interested and wishes to proceed, PIs will set up a formal screening appointment with the potential participant.
- d. A research assistant-trained by the PI will call potential participants referred by clinicians and caregivers who do not respond to email nor mail to tell them about the study using the IRB-approved phone script and ask screening questions. The name of the interested and potentially eligible participants will be given to the PIs. PIs will then set up a formal screening appointment with each potential participant. The research assistant will send the informed consent materials electronically to the potential participant through SendSafe/REDCap to review.

## II. Screening Phase

- a. PIs will meet with the potential participant over the phone to explain the study procedures and answer questions.
- b. PIs will begin the process of ensuring that participant meets eligibility criteria as outlined in Section 5.1. The [Sour Seven](#) questionnaire will be used to help determine whether a caregiver is a "dementia caregiver" or a "DSD caregiver" if a potential caregiver participant is unsure whether or not their loved one has had DSD within the past 12 months ("We are looking for two types of caregivers of persons with dementia. To help us better decide which category you would fit the best, we are going to ask you some additional screening questions. Thinking of the past 12 months, was there a change in your loved one's health status, such as hospitalization or a new infection? If so, do you recall observation of any of the following, right before, during, or after the hospitalization or the infection: ").
- c. PIs will probe for participant's ability to complete the duration of the study. These questions are used as indicators of potential early study dropouts. Potential caregiver participants' response to these questions will not be used to exclude them from study participation.
  - i. Is the participant planning to move within the next 6 months?
  - ii. Is the participant looking for a new job?
  - iii. Is the participant in the military, and/or do they have a spouse in the military?

## III. Consenting Phase

- a. If the caregiver is eligible and wishes to participate, PIs will then schedule a follow-up Zoom call with the caregiver within a week to complete the e-Consenting process together in REDCap. If the caregiver has not received a copy of the consent form from the research assistant, then PIs will email or mail a copy of the consent form to the potential caregiver participant in advance based on the caregiver's preference. Eligible caregivers can also choose to proceed to complete the e-Consenting process described below within the same Zoom call.
- b. During the Zoom call (HIPAA compliant Zoom), PIs will open a new REDCap e-consent form in REDCap, share the screen and go over the IRB-approved REDCap e-consent and HIPAA authorization form, page by page, with the caregiver. The eConsent link will be provided as soon as available for IRB review and before use with caregiver subjects. The e-consent process informs the potential caregiver participant about the study, describes potential risks and benefits, indicates that the participation is voluntary and that he/she has the right to stop at any time. The PIs will also provide the potential caregiver participant contact information in case of medical emergency due to study participation and questions about subject rights, as well as explain who have access to study data and protected health information (PHI), how confidentiality is maintained, how the participant may receive the outcome of the study and incentives for study participation. The PI consenting the caregiver will ensure that the eligible caregiver has the opportunity to consider whether to participate and ask questions before electronically signing the consent and HIPAA authorization forms in REDCap during the Zoom call, as well as at anytime during their involvement in the research study.

CONFIDENTIAL

This material is the property of the NYU Langone Health. Do not disclose or use except as authorized in writing by the study sponsor

If the caregiver decides to give consent, the PI consenting the caregiver will give the caregiver remote control over his/her mouse in his/her device to initial and sign the REDCap e-consent and HIPAA authorization form in REDCap. After signing electronically, the caregiver will receive an electronic copy of the signed consent and HIPAA authorization form immediately in an automatically generated email from REDCap. If a caregiver has difficulty signing the e-Consent form in REDCap using the PI's mouse via remote control, the PI will email the caregiver a link to the REDCap e-Consent form and have the caregiver open the consent form in their local device (computer, laptop, etc.) to initial and sign in REDCap. Caregivers enrolled in the feasibility study phase will have the option to include additional secondary caregivers, who will undergo the same e-Consenting process.

### 7.3.2 Enrollment/Baseline

Aim 1 codesign workshop: One 1:1 data collection visit will be scheduled and completed with each participant at baseline/enrollment (Week 0). The enrollment/baseline visit will be scheduled within 7 days from the time of informed consent. Participants can choose to complete the baseline/enrollment data collection in the same Zoom call in which they complete the eConsent. The following information will be collected in online REDCap survey questionnaires:

- ✓ Demographics
- ✓ Familiarity with DSD
- ✓ Health literacy
- ✓ Comfort with technology

Aim 2 feasibility trial: One 1:1 data collection visit will be scheduled and completed with each participant at baseline/enrollment (Week 0). The enrollment/baseline visit will be scheduled after the informed consent has been obtained and based on the participant's availability. Participants can choose to complete the baseline/enrollment data collection in the same Zoom call in which they complete the eConsent. The following information will be collected in online REDCap survey questionnaires:

- ✓ Demographics
- ✓ Dementia severity
- ✓ Behavioral symptoms
- ✓ Health literacy
- ✓ Caregiving self-efficacy
- ✓ Comfort with technology
- ✓ Strain
- ✓ Depression
- ✓ Burden
- ✓ Delirium knowledge
- ✓ DSD caregiver mastery

### 7.3.3 Intermediate Visits

Aim 1 codesign workshop: Caregiver participants will attend 5 weekly group co-design sessions (90-120 minutes/session) to discuss the following topics. The first group co-design session will be scheduled within

CONFIDENTIAL

This material is the property of the NYU Langone Health. Do not disclose or use except as authorized in writing by the study sponsor

a week after 8 participants have completed their baseline/enrollment visit. Each session will be video recorded along with live chat via HIPAA Compliant Zoom.

- *Session 1: family education videos*
- *Session 2: assessments and care plans*
- *Session 3: caregiver education articles and communication guides*
- *Session 4: mobile push notification or text messages to motivate/encourage caregivers*
- *Session 5: final design and features of the mHealth app; ways to best engage other family members in delirium care*

Aim 2 feasibility trial: The second 1:1 study visit will be scheduled in Week 2 (+/-5 days) to assess changes in delirium knowledge and DSD caregiving mastery immediately after each participant has completed the self-paced training videos on DSD in online REDCap survey questionnaires.

#### 7.3.4 Final Study Visit

Aim 1 codesign workshop: See 7.3.3 above for information about the fifth co-design session. An optional 30-minute, 1:1 user testing session will be scheduled with 5-6 volunteers from Aim 1 participants and waitlist to test the beta version of the new caregiver mHealth app developed based on co-design workshop feedback in-between the 2 study phases. The fifth co-design session and the 1:1 session will both be video recorded along with live chat via HIPAA Compliant Zoom.

Aim 2 feasibility trial: The final 1:1 study visit will be scheduled in Week 6 (+/-5 days) to collect data on the following using online REDCap survey questionnaires:

- ✓ Caregiver strain
- ✓ Depression
- ✓ Caregiver burden
- ✓ Caregiver delirium knowledge
- ✓ DSD caregiver mastery
- ✓ Program satisfaction
- ✓ App usability

#### 7.3.5 Withdrawal Visit

The PI or co-PI will email the subject up to 3 times and call the subject up to 3 times to obtain the reason(s) for the voluntary withdrawal. For Aim 2 participants, information on adverse events/serious adverse events suspected or experienced during their study participation will also be collected at this time. Reporting of adverse events/serious adverse events is not applicable to Aim 1 participants because the Aim 1 codesign workshop is not an interventional study.

#### 7.3.6 Unscheduled Visit

For the Aim 1 co-design workshop, a group attendance sheet will be maintained to log attendance of the five weekly codesign sessions, along with reasons for absence. A group co-design session will be rescheduled, or a makeup session will be provided, if most of the participants are not able to attend a particular scheduled group co-design session.

For the Aim 2 feasibility trial, data collection must be completed within +/- 5 days of each planned data collection session. Reasons for incomplete sessions will be documented in REDCap.

CONFIDENTIAL

This material is the property of the NYU Langone Health. Do not disclose or use except as authorized in writing by the study sponsor

## **7.4 Concomitant Medications, Treatments, and Procedures**

Not applicable.

## **7.5 Justification for Sensitive Procedures**

Not applicable.

### **7.5.1 Precautionary Medications, Treatments, and Procedures**

Not applicable.

## **7.6 Prohibited Medications, Treatments, and Procedures**

Not applicable.

## **7.7 Prophylactic Medications, Treatments, and Procedures**

Not applicable.

## **7.8 Participant Access to Study Intervention at Study Closure**

Not applicable.

# **8 Assessment of Safety**

## **8.1 Specification of Safety Parameters**

The following sections are only applicable to the Aim 2 feasibility trial because the Aim 1 codesign workshop is not an interventional study.

### **8.1.1 Definition of Adverse Events (AE)**

An **adverse event** (AE) is any symptom, sign, illness or experience that develops or worsens in severity during the course of the study. In this minimal risk study, the sole anticipated potential AE is breach of confidentiality and will be monitored for.

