## **2.3 Potential Risks & Benefits**

### **2.3.1 Known Potential Risks**

This is a minimal risk study. The intervention itself is inherently not risky as it is a family-centered, psychoeducational training program on implementation of evidence-based best practices through an mHealth app to improve family caregivers' mastery in performing DSD detection, prevention, and symptom management tasks. The greatest potential risks to family caregiver subjects are (1) a breach of confidentiality and (2) psychological distress.

Though possible, we anticipate that a breach of confidentiality is unlikely to happen because personal identifiers will only be collected and stored in the password-protected REDCap electronic consent and HIPAA authorization form, in which only authorized study team members will have access to, whereas all the other study data will be deidentified and stored in a password-protected NYU Box folder, in which access will only be granted to appropriate study team members. NYU Box is the NYU WSQ Campus approved storage of [high-risk data](#).

When learning something new such as a new mHealth app, some caregivers can become frustrated or experience psychological distress. However, we believe psychological distress is unlikely to happen, because we will have tested our mHealth app to ensure user-friendliness. We will also proactively offer additional technical support/training sessions on how to use the study app via Aliviado Support Center ([contact]) to caregivers who report a lower level of comfort with technology at enrollment (caregivers are free to decline this offer/additional support). If caregiver subjects experience psychological distress or become frustrated with the technology, they can contact Aliviado Support Center ([contact]) for assistance. If participants do not feel comfortable answering depressive symptom questions or any questions in any of the study questionnaires, they have the option to select "prefer not to answer" as their response. Subjects may also experience psychological distress when answering questions about their depressive symptoms and will also have the option to select "prefer not to answer".

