### **5.7.2 Handling of Participant Withdrawals or Termination**

The study team will ask participants to provide their reason(s) for termination and keep a termination log. The study team will email and call the participants for up to three times to obtain their reason(s) for termination; for Aim 2 participants, the study team will also ask participants to provide information on any adverse events/serious adverse events suspected/experienced during their study participation (this is not applicable to Aim 1 participants because Aim 1 is not an intervention study). To reduce the likelihood of participant withdrawals, the study team will clearly explain to potential caregiver participants the study procedures during screening and the consenting process, ensure accuracy of contact information of enrolled caregiver participants, query about any plans to move within the next 6 months, and allow flexibility in scheduling data collection sessions (i.e., scheduling the Aim 1 weekly codesign sessions to the day of the week most participants are availability; allowing +/- 5 days to complete each Aim 2 planned data collection session). Caregiver participants will be encouraged to contact the Aliviado Support Center at [[contact]](mailto:[contact]) for any questions, concerns, or technical support; questions and concerns about the study will be forwarded to the PIs; technical support will be provided by the Support Center staff.

For Aim 1 codesign workshop, we plan to maintain a waitlist of 8 caregivers in case some of the enrolled caregivers drop out of the study or are not able to complete all 5 weekly codesign sessions. Caregivers on the waitlist will be notified of openings of the weekly codesign sessions and will need to complete the standard eConsent procedure in order to attend the codesign sessions.

For Aim 2 feasibility trial, if there are more than 4 dropouts, we will continue to recruit additional caregivers until 26 primary caregivers have completed the study.

CONFIDENTIAL

This material is the property of the NYU Langone Health. Do not disclose or use except as authorized in writing by the study sponsor

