### **8.4.1 Adverse Event Reporting**

We recognize that some caregivers might experience psychological distress resulting from learning a new mHealth app during the feasibility trial. Therefore, we will passively monitor any psychological distress reported by caregivers. The term “passive” or “passively” refers to the reliance on voluntary caregiver report, in contrast to the study team’s administration of regular screening throughout the study period to “actively” monitor any changes in psychological distress in caregiver participants.

A summary of all adverse events and serious adverse events will be reported to the NIA Program Officer and the Safety Officer on a quarterly basis.

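### Psychological distress is missing from the anticipated adverse events in Section 8.1.1, and a direct adverse-event question is written only for caregivers who withdraw

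*Combined protocol and SAP*

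**What the plan says.** On the risks, Section 2.3.1 says: "The greatest potential risks to family caregiver subjects are (1) a breach of confidentiality and (2) psychological distress". It describes distress as arising from learning a new app or from answering the depressive-symptom questions. It calls both named risks unlikely.

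On anticipated AEs, Section 8.1.1 says that "the sole anticipated potential AE is breach of confidentiality and will be monitored for". The definition just before that statement is broad: any symptom, sign, illness or experience that appears or worsens during the study.

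On monitoring, Section 8.4.1 says: "We recognize that some caregivers might experience psychological distress resulting from learning a new mHealth app during the feasibility trial". It continues that "we will passively monitor any psychological distress reported by caregivers", and explains that passive "refers to the reliance on voluntary caregiver report", as opposed to regular screening. The same section sends a quarterly summary of all AEs and serious AEs to the NIA Program Officer and the Safety Officer.

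On asking about AEs, Section 5.7.2 says of Aim 2 withdrawals that "the study team will also ask participants to provide information on any adverse events/serious adverse events suspected/experienced during their study participation". Section 7.3.5 repeats this: "For Aim 2 participants, information on adverse events/serious adverse events suspected or experienced during their study participation will also be collected at this time".

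On depressive symptoms, Section 7.1.1 measures the CES-D at baseline and Week 6. If a caregiver's score rises by 15 or more points on the 60-point scale, the medical monitor calls, judges whether the change is related to study participation, and refers as needed. High CES-D or strain scores also lead to an offer of referral.

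**The concern.** There are two linked problems.

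First, the protocol contradicts itself on whether distress is an anticipated AE. The word for a single anticipated event in Section 8.1.1 cannot stand beside Sections 2.3.1 and 8.4.1, which both foresee a second one. Staff who work from the safety section would not be told to look for it.

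Second, the way AEs are found depends on whether the caregiver leaves. Someone who withdraws is to be asked directly. Someone who attends the Week 2 and Week 6 visits has no AE question in the written visit content.

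What is at stake is the completeness of a small safety record. Distress is the main risk other than loss of privacy. A pilot meant to prepare for a larger trial should be able to say how often it occurred. As written, a low count among caregivers who stay could mean little distress, or that nobody asked.

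**Working it through.** No power, sample-size or error-rate figure underlies this point. The check is a comparison of sections, with one piece of arithmetic for scale and one for the reach of the CES-D rule.

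**Step 1. Is distress anticipated?**

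| Section | Breach of confidentiality | Psychological distress |
|---|---|---|
| 2.3.1 | Named as a greatest risk, called unlikely | Named as a greatest risk, called unlikely |
| 8.1.1 | Anticipated AE, the only one | Not listed |
| 8.4.1 | Not discussed | Foreseen from learning the app, monitored passively |

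Likelihood does not explain the difference in Section 8.1.1, because Section 2.3.1 calls both risks unlikely. Nor does the definition of an AE, since distress that appears or worsens during the study fits it.

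**Step 2. Who is asked about AEs?**

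| Contact with an Aim 2 caregiver | AE question written? |
|---|---|
| Withdrawal (5.7.2, 7.3.5) | Yes |
| Week 2 visit (7.1.1, 7.3.3) | No: knowledge and mastery only |
| Week 6 visit (7.1.1, 7.3.4) | No: strain, depression, burden, knowledge, mastery, satisfaction, usability |
| Table 4 (14.1.1) and Aim 2 schedule (Attachment C) | No AE item |

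**Step 3. How many are asked?** Section 10.5 plans for 30 recruited, 12% dropout and 26 evaluable.

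- Dropouts: 30 × 0.12 = 3.6, or about 4. This agrees with 30 − 26 = 4.
- Share asked: 4/30 = 13%. Share not asked: 26/30 = 87%.

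At that dropout rate, 4 is a ceiling, because contact after withdrawal is limited to three emails and three calls and may fail. With full retention, nobody is asked. If more than 4 leave, Section 5.7.2 continues recruitment until 26 complete, so about 26 unasked completers is the planned result in that case too. Optional secondary caregivers (0 to 30) are left out, as the plan gives no dropout rate for them.

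**Step 4. What does the CES-D rule cover among those who stay?** It is a real, active check, but a narrow one.

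- It covers depressive symptoms, not frustration or anxiety over the app.
- It is applied once, at Week 6, so distress that resolves earlier is missed.
- It needs a rise of 15 or more on a 60-point scale. Since 60 − 15 = 45, a caregiver with a baseline score above 45 cannot reach it.
- Under Section 2.3.1 a caregiver may decline to answer any question, which can remove the score.
- Section 7.1.1 does not say that a triggered case becomes an AE record.

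In caregivers who stay, then, distress outside that rule reaches the AE record mainly if the caregiver raises it.

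**The case against.** The strongest reply is that passive monitoring is a disclosed choice in a minimal-risk study. Section 8.4.1 defines the term and contrasts it with active screening. Section 8.5 leaves AE definitions and monitoring frequency to the Safety Officer, with a data safety monitoring plan to be attached after approval. Section 8.7 has the Safety Officer approve the safety data elements, and has the medical monitor assess psychological symptoms that are identified. Section 8.2.2 adds that doubtful cases should be reported. A final procedure may therefore fill the gap. This part stands as a caution: the procedure actually used may be better than the text. It does not repair the text. Section 8.1.1 is the current definition, and the attachments listed in Section 19 (A to D) do not include that plan.

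Three stronger readings are tempting, and the documents do not support them.

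- A reader might infer that distress in caregivers who stay is captured only if volunteered. The CES-D rule in Section 7.1.1 is an active check with a relatedness judgement, so that goes too far.
- A reader might infer that whether an event is reportable depends on which section is read. Section 8.2.3 judges expectedness against the risk information already described, and Section 8.1.3 looks to study documents including the protocol. Distress of the kind in Section 2.3.1 is described there, so its omission from Section 8.1.1 does not make it unexpected. Section 8.4 reports related AEs, and the quarterly summary in Section 8.4.1 covers all AEs. Neither filters AEs by expectedness.
- A reader might infer that AE rates in completers and dropouts will be compared and the comparison biased. Section 10.4.4 plans no safety analysis, and about 4 against 26 people would support no such comparison.

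**Conclusion.** The point holds in limited form. Section 8.1.1 conflicts with Sections 2.3.1 and 8.4.1 and must be reconciled with them. A direct AE question is written only for withdrawals. Among caregivers who stay, distress other than a CES-D rise of 15 or more at Week 6 rests on voluntary report, and it is not stated that even a triggered case is recorded as an AE. The AE counts in the quarterly summaries will therefore partly reflect who was asked.

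The scale is about 4 of 30 primary caregivers asked and about 26 not. This assumes the planned 12% dropout and that every caregiver who withdraws is reached. How many events would be missed cannot be derived, because the documents give no rate of distress. The conclusion also assumes that the data safety monitoring plan, which is not part of the text, adds no AE question at the study visits. The primary endpoints and the planned tests are unaffected.

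**What to change.** Make three changes.

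1. Reconcile Section 8.1.1 with Sections 2.3.1 and 8.4.1 by listing psychological distress as an anticipated AE beside breach of confidentiality.
2. Put the AE question already used at withdrawal to every Aim 2 caregiver at the Week 2 and Week 6 visits, record the answer on the AE form, and add the item to the Aim 2 schedule in Attachment C. Amend Section 8.4.1 so that it no longer describes monitoring as purely passive.
3. State in Section 7.1.1 whether a case found by the CES-D rule is logged as an AE.

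The cost is one question at two 1:1 visits that already take place, plus wording. No extra staff or visits are needed. Recorded AE counts may rise because people are being asked, and the quarterly summary should say so. This is a cheap improvement. It makes AE ascertainment the same for caregivers who stay and those who leave.
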